The main hypotheses for these parts of the study are that PASC have positive impact on patients experiences with using the checklist and the implementation of it. Hence, primary outcomes of these two studies are the PASC experience questionnaire (PASC-EQ) and the PASC implementation questionnaire (PASC-IQ).

The survey instruments

The PASC-EQ instrument was developed to measure patients' experiences with using the patient safety checklist in the intervention arm ([name] 2017). The development was based on literature searches (Harris et al. 2020, Harris et al. 2022) and expert review of items suggested

by the research group. Items were reviewed by clinicians and researchers within patient safety and surgical safety checklists research group of PASC.

The PASC-EQ consists of 21 items representing 5 domains of patients' experiences with using the patient safety checklist (PASC). The domains are labelled as 1: Information on my surgery. 2: Patient safety. 3: Patient involvement. 4: Communication with healthcare personnel. 5: Engaging with healthcare services.

For the PASC Implementation Questionnaire (PASC-IQ) we added three dimensions, each with four items, to the survey. These items were inspired by the implementation form used by Weiner and colleagues (2017) and adapted for investigating the PASC implementation experiences.

For both questionnaires, all scores went from 'Disagree totally', 'Disagree', 'Nor disagree or agree', 'Agree', and 'Agree totally' (values 0-4).

Statistical power of the PASC trial on the PASC-EQ and PASC-IQ

According to Kline (2011, p. 225) the sample size required to perform Structured Equational Modelling (SEM) usually requires 3-400 cases for models when degrees of freedom are <10. With higher degrees of freedom, i.e. > 20, a smaller number of cases is required for a minimum power of 0.80. However, the sample size should never be less than 100 in any event (Kline, 2011). The degrees of freedom within PASC-EQ/PASC-IQ data, including 7 surgical clusters, are estimated to be 32. Accordingly, more than 200 cases (respondents) are a sufficient sample for conducting SEM (confirmatory factor analysis) with PASC-EQ/PASC-IQ data.

Statistical analysis

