d. Effect size measured by the root-mean-square standardized effect.

Statistical analysis

Descriptive statistics (i.e. frequencies, percentages, mean, standard deviations) will be used to assess responding patients' characteristics, clinical variables, and surgical specialties (i.e. comorbidity, type of anesthesia or surgery, length of surgery) and EQ-5D-3L dimensions. To investigate the PASC intervention effect on EQ-5D-3L, a chi-squared test will be used to test any differences on patient characteristics between the trial arms. General Linear model with analysis of covariance will be used to investigate mean score difference between control and intervention arms. If there are significant variations in patients' characteristics and clinical variables between the two arms adjustments for these differences will be applied in the regression model to compare effects across the domains (Jansson, 2011). All analysis will be performed in SPSS 29.0 (IBM Corp, Armonk, NY) and a two-sided P value at 0.05 will be considered statistically significant.

The validity and reliability of the EQ-5D-3L will be investigated. The internal consistency will be measured by using Cronbach's alpha (scores between 0 and 1, preferably >0.7) and Pearsons' correlation or Spearman's rho as appropriate. Psychometric evaluation will be performed by measuring the hypothesized structure model of the EQ-5D-3L with fit indicators as χ^2 , CFI, TLI, and RMSEA (Bollen 1989, Kline 2011). The analysis will be performed in IBM SPSS version 29 and IBM SPSS AMOS version 26.

According to Kline (2011, p. 225) the sample size required to perform Structured Equational Modelling (SEM) usually requires 3-400 cases for models when degrees of freedom are <10. With higher degrees of freedom, i.e. > 20, a smaller number of cases is required for a minimum power of 0.80. However, the sample size should never be less than 100 in any event (Kline, 2011). The degrees of freedom within EQ-5D-3L, including 7 surgical clusters are anticipated to exceed this number on degrees of freedom. Accordingly, in all, more than 200 cases (respondents) are sufficient sample for conducting SEM (confirmatory factor analysis) with the EQ-5D-3L data. Missing data will be managed by creating 200 imputed datasets and the imputation model included all variables that to be included in adjusted regression model.

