According to Kline (2011, p. 225) the sample size required to perform Structured Equational Modelling (SEM) usually requires 3-400 cases for models when degrees of freedom are <10. With higher degrees of freedom, i.e. > 20, a smaller number of cases is required for a minimum power of 0.80. However, the sample size should never be less than 100 in any event (Kline, 2011). The degrees of freedom within PASC-EQ/PASC-IQ data, including 7 surgical clusters, are 32. Accordingly, more than 200 cases (respondents) are sufficient sample for conducting SEM (confirmatory factor analysis) with PASC-EQ/PASC-IQ data. Missing data will be managed by creating 200 imputed datasets and the imputation model included all variables that to be included in adjusted regression model.

The sample size calculation and the statistical analysis plan to be used on HLQ data were described in protocol version 2.0. The SAP was up-dated 30th August 2024. The original statistical plan and the update was made by [name] [name], Department of Anaesthesia and Intensive Care, Haukeland University Hospital, Bergen, Norway; and Faculty of Health Sciences, Department of Nursing and Health Promotion, Acute and Critical Illness, Oslo Metropolitan University, Oslo, Norway.

References

- Boge RM, [name], [name] RM, Bruvik F, Harthug S. Discharge care quality in hospitalised elderly patients: Extended validation of the Discharge Care Experiences Survey. *Plos One*. 2019, 14(9):e0223150.
- Bollen K. Structural equations with latent variables. Wiley-Interscience publication. Mexico. 1989. ISBN 0-471-01171-1.
- Osborne RH, et al. The grounded psychometric development and initial validation of the Health Literacy Questionnaire (HLQ). *BMJ Public Health* 2013;13(658).
- Wahl AK, Hermansen Å, Osborne RH, Larsen MH. A validation study of the Norwegian version of the Health Literacy Questionnaire: a robust nine-dimension factor model, *Scand. J. Public Health*. 2021, 49(4):471-478.
- Kline RB. Principles and Practice of Structural Equation Modeling. Third edition. The Guilford Press. New York, USA, 2011.

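### The degrees of freedom behind the factor-analysis sample sizes are wrong or unsupported: the EQ-5D-3L model described has 5 (9 with the VAS), so the SAP's own rule asks for 300-400 respondents, and the 32 given for PASC-EQ/PASC-IQ cannot be reproduced

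*SAP*

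**What the plan says.** The SAP gives the same sample-size rule for structural equation modelling in three places: the power section for PASC-EQ and PASC-IQ, plan e) for the EQ-5D-3L, and plan f) for the HLQ. Such modelling "usually requires 3-400 cases for models when degrees of freedom are <10". Next: "With higher degrees of freedom, i.e. > 20, a smaller number of cases is required for a minimum power of 0.80". There is also a floor: "the sample size should never be less than 100 in any event".

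The rule is then applied as follows.

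- **EQ-5D-3L (plan e).** "The degrees of freedom within EQ-5D-3L, including 7 surgical clusters are anticipated to exceed this number on degrees of freedom". No figure is given. The conclusion is that "more than 200 cases (respondents) are sufficient sample for conducting SEM (confirmatory factor analysis) with the EQ-5D-3L data". The analysis itself is described as "measuring the hypothesized structure model of the EQ-5D-3L with fit indicators" (chi-squared, CFI, TLI and RMSEA).
- **PASC-EQ and PASC-IQ.** The degrees of freedom, "including 7 surgical clusters, are estimated to be 32", and more than 200 respondents are again called sufficient.
- **HLQ (plan f).** The paragraph closing the HLQ analysis reads "The degrees of freedom within PASC-EQ/PASC-IQ data, including 7 surgical clusters, are 32", and its conclusion is also about PASC-EQ/PASC-IQ data. No df and no required sample are given for the HLQ.

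No model, parameter count or derivation is shown for any of these figures.

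**The concern.** The rule turns on the df of the fitted model, so the df decide which sample size applies. In a confirmatory factor analysis (CFA) they follow from the number of indicators and free parameters. The number of wards adds nothing unless wards are built into the model as groups or covariates. With only five items, the EQ-5D-3L has few df and falls in the class for which the SAP asks for the larger sample, not the smaller one.

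At stake is whether the SAP's stated minimum for the EQ-5D-3L factor analysis agrees with its own criterion, and whether the PASC-EQ/PASC-IQ and HLQ samples have a justification that a reader can check. As written, an EQ-5D-3L factor analysis on slightly more than 200 respondents would count as adequately sized when the SAP's rule says otherwise.

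**Working it through.** **Inputs, all from the SAP.** EQ-5D-3L: five dimensions plus a visual analogue scale (VAS). PASC-EQ: 21 items, 5 domains. PASC-IQ: 3 dimensions of 4 items, so 12 items. HLQ: 44 items, 9 domains. Seven surgical clusters. Anticipated EQ-5D-3L respondents: 125 + 200 = 325.

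**Formula.** For p items, each loading on one of f correlated factors, with factor variances fixed at 1:

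- moments = p(p+1)/2
- free parameters = p loadings + p error variances + f(f-1)/2 factor covariances
- df = moments - parameters

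Adding intercepts adds p moments and p parameters, so df do not change.

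Two ways in which wards could enter are also shown:

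- seven groups with the same structure and no equality constraints: 7 x df
- six ward indicators as covariates: (p+6)(p+7)/2 - [2p + f(f-1)/2 + 6f + 21]

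| Model | p, f | Moments - parameters | df | Seven groups | Six ward covariates |
|---|---|---|---|---|---|
| EQ-5D-3L | 5, 1 | 15 - 10 | **5** | 35 | 66 - 37 = 29 |
| EQ-5D-3L with VAS | 6, 1 | 21 - 12 | **9** | 63 | 39 |
| PASC-EQ | 21, 5 | 231 - 52 | **179** | 1253 | 275 |
| PASC-IQ | 12, 3 | 78 - 27 | **51** | 357 | 105 |
| PASC-EQ and PASC-IQ together | 33, 8 | 561 - 94 | **467** | 3269 | 617 |
| HLQ | 44, 9 | 990 - 124 | **866** | 6062 | 1076 |

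**Trying to reproduce the SAP's figures.**

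1. *EQ-5D-3L above 20.* Not reached by a single-group model. One factor gives 5 and two factors give 15 - 11 = 4; with the VAS these become 9 and 8. All are below 10, so the conclusion is the same whether the number to be exceeded is read as 20 or as 10.
2. *PASC-EQ/PASC-IQ equal to 32.* No column of the table gives it. One-factor models (189 for PASC-EQ, 54 for PASC-IQ) and second-order models (184 for PASC-EQ, 487 for both together) do not either. Eight domain scores on one factor give 36 - 16 = 20. A simple-structure model with 10 items and 3 factors has 55 - 23 = 32 df, but no instrument here has that shape. The number also equals 21 + 12 - 1, the item count less one, which is not a CFA df.
3. *HLQ.* The item-level model has 866 df. Nine domain scores on one factor would give 45 - 18 = 27. Neither is 32.

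**Applying the SAP's rule to the recomputed df.**

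- EQ-5D-3L: 5 or 9 df is below 10, so 300-400 cases. The anticipated 325 lies inside that range, as does the original 200 + 200 = 400.
- PASC-EQ, PASC-IQ and HLQ: 179, 51 and 866 are all above 20, the class in which fewer cases are asked for.

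**Expected HLQ respondents.** 350 + 350 = 700 patients are surveyed. At the 35% response given in plan f), 0.35 x 700 = 245. At the 50% given in the health-economic section, which refers back to the HLQ calculation, 0.50 x 700 = 350.

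**The case against.** The strongest reply is that the SAP does not fix the model and expressly counts the seven clusters. A seven-group EQ-5D-3L model has 35 df and one with six ward covariates has 29, both above 20 as the SAP anticipates. A reader might therefore infer either that the SAP is right, or, at the other extreme, that the EQ-5D-3L can never have more than 5 df. Neither follows. The SAP names no multi-group, invariance or covariate analysis, and the one model it describes has 5 df. Nor does either convention give 32 for the PASC questionnaires, so no single reading supports both statements. It would be wrong, however, to reject the seven-group reading on the ground that 325/7 is about 46 per ward and below the floor of 100: the SAP sets that floor for the sample size and counts its EQ-5D-3L cases in all.

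Three further objections stand and limit the point.

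- A reader might infer that the EQ-5D-3L survey is too small. The anticipated 325 meets the SAP's own 300-400.
- A reader might infer that the wrong 32 undermines the other samples. It does not: the recomputed df are all larger than 32, so under the SAP's rule more than 200 is not overturned for PASC-EQ, PASC-IQ or HLQ.
- One could call the HLQ sample inadequate because 245 respondents for 124 parameters is about 2.0 each. The SAP contains no threshold per parameter, so that is no contradiction within the document.

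**Conclusion.** The point holds as an error in the written justification. For the single-group CFA that plan e) describes, the EQ-5D-3L has 5 df (9 with the VAS) against a claimed value above 20, and the SAP's rule then asks for 300-400 respondents rather than more than 200. The 32 df for PASC-EQ/PASC-IQ is unsupported by any item-level model of those questionnaires, and the HLQ section carries that sentence over with no figure for the HLQ.

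This rests on simple-structure models with the item and domain counts in the SAP and on the SAP's own sample-size rule taken as given. The cited textbook was not available to check the rule itself.

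The practical effect is low. The anticipated EQ-5D-3L sample already meets the lower end of the correct range. Only the psychometric analyses are concerned: no treatment-effect analysis depends on these df, including the EQ-5D-3L and HLQ comparisons between arms, whose sample sizes are calculated separately. The correction is still worth making, because the SAP relies on these figures to call its samples sufficient.

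**What to change.** 1. In all three places, remove the reference to the seven surgical clusters from the df statement, or specify the model in which wards enter and give its df.
2. State the CFA model and df for each instrument: EQ-5D-3L 5 (9 if the VAS is an indicator), PASC-EQ 179, PASC-IQ 51, HLQ 866.
3. In plan e), replace the threshold of more than 200 with the SAP's 300-400, note that the anticipated 325 meets its lower end, and say that the EQ-5D-3L factor analysis will be labelled exploratory if fewer than 300 respond.
4. In plan f), replace the PASC-EQ/PASC-IQ sentences with an HLQ statement: 866 df for the nine-factor model, with 245-350 respondents expected at 35%-50% response.

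Splitting the HLQ into nine one-factor models is not a remedy. With 44 items in 9 domains the average is under 5 items per domain, and one-factor models of 4, 5 and 6 items have 2, 5 and 9 df. Most would fall in the class needing 300-400 cases, and the nine-dimension structure would go untested.

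The cost is a few lines of SAP wording. No data collection or recruitment target changes.

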The main goals of the study are to investigate the impact of a patient safety checklist on patients having surgery within different surgical specialties, in three Norwegian hospitals (rural, central, and university hospital). The study has several work packages and hypothesis: a) The PASC checklist is hypothesized to have effect on surgical patients’ complications, reoperations, readmissions, length of stay and mortality. Of these variables, complications are the primary outcome. Further, patients’ experiences are hypothesized to be positively impacted by using PASC. Primary outcome for this part is the Patient Safety Checklist Experience Questionnaire. b) One part of the PASC checklist project include patients’ self-screening on their risk of malnutrition, prior to surgery. Main hypothesis is that the PASC have impact on nutritional outcomes. Nutritional complications are a primary outcome for this part of the study, and secondary outcome are comparison of patients and healthcare staffs’ risk assessments by comparing use of the Malnutrition Screening Tool. c) Investigate how implementation of the PASC checklist, a patient safety intervention, may be optimally used by the patients. Primary outcome is feasibility and compliance to using the checklist. Further, patients experiences are hypothesized to be positive towards the implementation. Primary outcome of this part is the PASC implementation survey. d) PASC is hypothesized to have an impact on cost-benefit of patients and the healthcare services. For this part of the study, the primary outcome is cost-effectiveness of the implementation across a-c. Secondary outcomes are the patient costs attributed associated with their surgical treatment. e) The PASC checklist is hypothesized to have impact on patients’ health literacy. Primary outcome is the nine dimensions of the Health Literacy Questionnaire. f) PASC is hypothesized to have impact on patients’ Quality of Life. Primary outcome is the EuroQual-5D-3L questionnaire.

Explanations of the statistical analysis techniques used for analyzing the data in the trial are detailed in the pages below.

Reference

Harris et al. Development and validation of patients’ surgical safety checklist. BMC Health Services Research. 2022; 22:259.

Statistical analysis plan a) for the PASC Stepped Wedge Cluster Randomized Controlled Trial

Hypothesis

[figure not shown]

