The sample size calculation and the statistical analysis plan to be used on EQ-5D-3L data were described in protocol version 2.0 (30th June 2021), along with the description of statistical analysis of the HLQ survey, and updated 30th August 2024, by [name] [name], Department of Anaesthesia and Intensive Care, Haukeland University Hospital, Bergen, Norway; and Faculty of Health Sciences, Department of Nursing and Health Promotion, Acute and Critical Illness, Oslo Metropolitan University, Oslo, Norway.

References

- Bollen K. Structural equations with latent variables. Wiley-Interscience publication. Mexico. 1989. ISBN 0-471-01171-1.
- Jansson K-Å, Granath F. Health-related quality of life (EQ-5D) before and after orthopedic surgery. *Acta Orthopaedica* 2011; 82(1):82-89.
- Kline RB. Principles and Practice of Structural Equation Modeling. Third edition. The Guilford Press. New York, USA, 2011.

Statistical analysis plan f) for PASC impact on patients' health literacy

The main hypothesis is that PASC improve surgical patients' health literacy. The primary outcome is the nine dimensions in the Health Literacy Questionnaire (HLQ), developed by Osborn et al 2013).

Statistical power and sample size required for HLQ in the PASC trial

A power analysis was performed to assess the required number of participants in the survey. It was based on mean score results in a previous Norwegian study of health literacy in a population of patients with skin diseases (Wahl, 2021). The lowest number of individuals required to detect a clinical meaningful mean score difference at 0.30 between the baseline and intervention groups would be $n = 103$ patients in each arm of the PASC trial. A standard deviation at 0.66 in both arms were assumed. Power was estimated at 90% and a type I error at 0.05. Previous research experiences on surveys in Norwegian hospitals indicate that patients' responses could possibly be 35% (Boge, 2019). Hence, we include 50 patients per cluster with a total of 350 patients in the baseline group and 350 patients in the intervention group to ensure enough respondents.

The survey instrument

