The HLQ consists of 44 questions with 9 domains that represent patients' health literacy. The domains are labelled as 1: Understood and supported by health professionals. 2: Satisfactory information to handle own health. 3: Active management of own health. 4: Social support of own health. 5: Consider health information. 6: Active cooperation with health professionals. 7: Navigation through the healthcare system. 8: Possibilities to find right health information and 9: Understand the health information to be able to know what should be done.

Statistical analysis

Descriptive statistics (i.e. frequencies, percentages, mean, standard deviations) will be used to assess patients' characteristics (i.e. age, gender, comorbidity, educational level, societal status). To investigate the PASC intervention effect on health literacy, a chi-squared test will be used to test any differences between the trial arms. General Linear Model will be used to investigate mean score difference between control and intervention arms. If there are significant variation in patients' characteristics between the two arms a linear regression model will be applied to adjust for it and to compare effects across the nine domains on health literacy (Osborne, 2013).

All analysis will be performed in SPSS 29.0 (IBM Corp, Armonk, NY) and a two-sided P value at 0.05 will be considered statistically significant.

Validity and reliability of the HLQ will be investigated. The internal consistency will be measured by using Cronbach's alpha (scores between 0 and 1, preferably >0.7) and Spearman's rho for correlations between the dimensions. Psychometric evaluation will be performed by measuring the hypothesized structure model of the HLQ with fit indicators as χ^2 , CFI, TLI, and RMSEA (Bollen 1989, Kline 2011). This analysis will be performed in IBM SPSS version 29 and IBM SPSS AMOS version 26.

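### Plan f ties one health literacy hypothesis to nine primary HLQ dimensions at two-sided 0.05 with no success rule or multiplicity control, and its 90% power covers a single unadjusted dimension.

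*SAP*

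**What the plan says.** The section headed Statistical analysis plan f) states a single hypothesis: "The main hypothesis is that PASC improve surgical patients' health literacy". The outcome attached to it is plural: "The primary outcome is the nine dimensions in the Health Literacy Questionnaire (HLQ"). The SAP's opening overview agrees, although it letters this part e: "Primary outcome is the nine dimensions of the Health Literacy Questionnaire".

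Under Statistical analysis in plan f, a General Linear Model compares mean scores between arms. If patient characteristics differ between arms, an adjusted linear regression is used "to compare effects across the nine domains on health literacy". For all of this, "a two-sided P value at 0.05 will be considered statistically significant".

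The sample size paragraph is built on one mean difference: "The lowest number of individuals required to detect a clinical meaningful mean score difference at 0.30 between the baseline and intervention groups" is given as 103 per arm. Its other inputs are: "A standard deviation at 0.66 in both arms were assumed" and "Power was estimated at 90% and a type I error at 0.05". A 35% response is expected, so 350 patients per group are to be surveyed.

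Plan f names no lead dimension, total score, global test, testing order or multiplicity procedure. It does not say whether one, several or all nine dimensions must reach significance.

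**The concern.** Plan f is set out as a confirmatory analysis, with its own main hypothesis, primary outcome, power calculation and significance threshold. With nine primary tests and no rule for combining them, the threshold of 0.05 does not fix the error rate of the conclusion that PASC improves health literacy. An author who finds one or two of nine dimensions below 0.05 could report support for the hypothesis without departing from the plan.

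The power statement has the matching gap. It describes one comparison at 0.05, whereas the claim rests on nine. Whichever success rule is eventually used, the 90% does not describe the chance of meeting it.

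**Working it through.** **Inputs.** From plan f: nine dimensions, two-sided 0.05, difference 0.30, SD 0.66, 103 per arm, 350 surveyed per group, 35% response. From plan d (PASC-HEI): 50 per cluster in each arm, 700 in all, with a 50% response rate, citing the HLQ and EQ-5D-3L calculations. From the EQ-5D-3L plan: 125 control and 200 intervention respondents anticipated at the 30 August 2024 update. The correlation between dimensions is not given, so it is varied here as an assumption.

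**Step 1: reproduce 103 per arm.** The normal approximation is n = 2(1.960 + 1.282)² × (0.66/0.30)² = 101.7, rounded up to 102. The two-sample t calculation gives 102.7, rounded up to 103. Power at 103 per arm by the noncentral t is 90.1%. The SAP's figure is correct for one dimension tested once at 0.05.

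**Step 2: error rate if any significant dimension counts.** For independent dimensions:
- either direction: 1 − 0.95⁹ = 0.370;
- improvement only: 1 − 0.975⁹ = 0.204.

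For a common correlation ρ, each of the nine null test statistics is written as √ρ·U + √(1−ρ)·Eⱼ, with U and Eⱼ independent standard normal. With c = 1.96, the either-direction rate is

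1 − ∫ φ(u) [Φ((c − √ρ·u)/√(1−ρ)) − Φ((−c − √ρ·u)/√(1−ρ))]⁹ du.

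The improvement-only rate drops the second Φ term.

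| Assumed ρ | False result, either direction | False improvement only |
|---|---|---|
| 0 | 37.0% | 20.4% |
| 0.5 | 26.9% | 13.5% |
| 0.7 | 20.2% | 10.1% |
| 0.8 | 16.6% | 8.3% |
| Single test | 5% | 2.5% |

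**Step 3: power per dimension at 0.05/9 = 0.00556.** Noncentral t, difference 0.30, SD 0.66:

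| Respondents | Source | Power at 0.05 | Power at 0.05/9 |
|---|---|---|---|
| 103 + 103 | Stated minimum | 90% | 68% |
| 122 + 122 | 0.35 × 350 = 122.5 | 94% | 77% |
| 125 + 200 | Stated for EQ-5D-3L, assumed to apply to HLQ | 98% | 88% |
| 175 + 175 | 0.50 × 350, if plan d's 50% applies to the 350 surveyed | 99% | 93% |

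For 90% power at 0.05/9, 162 per arm are needed. Holm rejects everything that Bonferroni rejects and sometimes more, so the last column is a lower bound for Holm. None of these figures allows for clustering, and neither does the SAP's HLQ calculation.

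**Step 4: the opposite success rule.** If all nine dimensions had to be significant and each truly shifted by 0.30, power at 103 per arm (normal approximation) would be 0.9035⁹ = 40% for independent dimensions and 71% at ρ = 0.7. The error rate would then not be inflated, but power would be well below 90%.

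**The case against.** **Any one dimension suffices.** A reader might infer that, as written, one dimension of nine below 0.05 establishes the claim. The SAP does not say so; the success rule is undefined. The error rates in step 2 are therefore conditional on that reading. Nor does the SAP say outright that the General Linear Model is run as nine separate univariate tests, though this is the likely meaning.

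**A false claim of improvement in 20% to 37% of cases.** A reader might take the either-direction figures this way. They include false worsening, and the hypothesis is about improvement. The relevant rates are about half as large. The 37% also needs independence, which is implausible for nine scales of one questionnaire; plan f itself intends to examine correlations between the dimensions. This objection stands as to size, but 8% to 14% at correlations of 0.8 to 0.5 is still several times 2.5%.

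**Controlling the nine tests must destroy the power.** A reader might infer this from the 68%. But 103 is the minimum, not the number surveyed, and other respondent figures in the SAP lead to 88% or 93% even under Bonferroni. Those figures carry their own assumptions: 125 and 200 are stated for EQ-5D-3L, and plan d's wording leaves open whether its 50% applies before or after the count of 700. What stands is that the loss may be modest.

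**The HLQ is a profile of nine scales, and this is a survey part of a trial whose primary outcome is complications.** Reporting nine estimates is reasonable, and the place of this part in the trial limits the weight of the point. It does not remove it, because plan f makes all nine dimensions primary for one hypothesis and sets a significance threshold.

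**Conclusion.** The concern holds in a limited form. Plan f leaves undefined what counts as success across nine primary dimensions and does not control the error rate over them. If any significant dimension is taken as support, the chance of a false improvement finding is about 20% under independence and about 14%, 10% or 8% at assumed common correlations of 0.5, 0.7 or 0.8, against 2.5% per test. The either-direction rates are 37%, 27%, 20% and 17%.

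The sample size arithmetic is right, but its 90% belongs to one unadjusted dimension. At 0.05/9 the power per dimension is 68% at the stated minimum and 77% to 93% at the respondent numbers derived from the SAP. It is therefore not established that the survey is underpowered once the tests are controlled. These results rest on the SAP's difference and SD, on assumed correlations and on independent patients; clustering could lower the power figures. The change is worth making because it is cheap. It does not affect the trial's main clinical outcome.

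**What to change.** In plan f:

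1. State that the primary claim is assessed with the Holm procedure across the nine HLQ dimensions at an overall two-sided 0.05, and that the claim refers to the dimensions that pass. Unadjusted 95% confidence intervals may still be shown for all nine.
2. State beside n = 103 that the 90% power is for a single unadjusted dimension, and give the power at the adjusted level for the expected number of respondents.
3. Do not name one dimension as primary at this stage unless it can be shown that the choice was made before any results were seen. Data collection began on 1 November 2021, plan a numbers the months of surgery 1 to 27, and plan f was updated on 30 August 2024. The survey data were therefore probably already collected by then, and such a choice could be data-driven.

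The cost is SAP wording and somewhat lower power per dimension, which Holm limits. No new patients or data are needed.
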